## Summary

**Introduction:** COVID-19 is an emerging pandemic disease caused by severe acute respiratory syndrome (SARS-CoV-2). Although most patients infected with SARS-CoV-2 are asymptomatic or have mild symptoms, some patients develop severe symptoms that can long-term impair their quality of life and functional capacity. SARS-CoV-2 is closely related to severe acute respiratory syndrome (SARS) with direct and indirect effects on several systems, especially the musculoskeletal system, in addition to the respiratory system. Some of these symptoms persist for a long time, called Post-Covid-19 Syndrome, directly interfering with the functional capacity and quality of life of these patients. Pilates exercises focus on breathing, postural symmetry, trunk stabilization, flexibility, joint mobility and strengthening through the full range of motion of all joints and not isolated muscle groups. **Objectives:** The objective of this study will be to evaluate the clinical and functional effects of a Pilates exercise program for patients with Post-Covid-19 syndrome after a period of intensive care admission and invasive mechanical ventilation. **Methods:** The study will be a clinical, randomized and controlled trial. 48 patients of both sexes, over 18 years of age, who have developed the severe form of COVID-19 and required at least 7 days of invasive mechanical ventilation will be recruited. Patients who currently require supplemental oxygen at home and who present motor, cognitive or neurological alterations that prevent the practice of Pilates will be excluded. They will be previously randomized in a 1:1 ratio by electronic system and blindly allocated to the intervention group that will perform an exercise protocol based on the Pilates method, 2x/week, for 12 weeks in therapeutic sessions of identical protocols lasting 60 min. All patients will be evaluated before and after for peripheral muscle strength and endurance, post-Covid-19 functional status, dyspnea, fatigue and quality of life. Data analysis will be performed using the SPSS 23.0 program ( *Statistical Package for Social Sciences* ). Descriptive analysis will be performed for all variables (mean and standard deviation). *General Linear Model* ( GLMs ) with mixed design will be performed to compare treatment effect size between groups. The *pairwise comparison comparisons* ) will be performed to verify the mean difference between the Pilates Group and the Control Group in all variables in each period independently. Intention-to-treat analysis was used using the *Last method. observation Carried Forward* (LOCF) for lost participant data. A significance level of 0.05 and a confidence interval of 95% will be adopted. **Results:** The expected results are based on the alternative hypothesis that Pilates exercises are clinically effective, improving functional performance, exercise tolerance, balance, reducing symptoms and improving the quality of life of patients with symptoms of Post-Covid-19 Syndrome.

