CoV-2 is closely related to severe acute respiratory syndrome (SARS) with direct and indirect effects on several systems, especially the musculoskeletal system, in addition to the respiratory system. Some of these symptoms persist for a long time, called Post-Covid-19 Syndrome, directly interfering with the functional capacity and quality of life of these patients. Pilates exercises focus on breathing, postural symmetry, trunk stabilization, flexibility, joint mobility and strengthening through the full range of motion of all joints and not isolated muscle groups. **Objectives:** The objective of this study will be to evaluate the clinical and functional effects of a Pilates exercise program for patients with Post-Covid-19 syndrome after a period of intensive care admission and invasive mechanical ventilation. **Methods:** The study will be a clinical, randomized and controlled trial. 48 patients of both sexes, over 18 years of age, who have developed the severe form of COVID-19 and required at least 7 days of invasive mechanical ventilation will be recruited. Patients who currently require supplemental oxygen at home and who present motor, cognitive or neurological alterations that prevent the practice of Pilates will be excluded. They will be previously randomized in a 1:1 ratio by electronic system and blindly allocated to the intervention group that will perform an exercise protocol based on the Pilates method, 2x/week, for 12 weeks in therapeutic sessions of identical protocols lasting 60 min. All patients will be evaluated before and after for peripheral muscle strength and endurance, post-Covid-19 functional status, dyspnea, fatigue and quality of life. Data analysis will be performed using the SPSS 23.0 program (Statistical Package for Social Sciences). Descriptive analysis will be performed for all variables (mean and standard deviation). General Linear Model (GLMs) with mixed design will be performed to compare treatment effect size between groups. Pairwise comparisons will be performed to verify the mean difference between the Pilates Group and the Control Group in all variables in each period independently. Intention-to-treat analysis was used using the Last Observation Carried Forward (LOCF) method for data on lost participants. The significance level of 0.05 and a confidence interval of 95% will be adopted. **Results:** The expected results are based on the alternative hypothesis that Pilates exercises are clinically effective, improving functional performance, exercise tolerance, balance, reducing symptoms and improving the quality of life of patients with symptoms of Post-Covid-19 Syndrome.

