### **1.1.8 respiratory disorders**

fibrotic normalities , previously associated with the idiopathic cause, are the main consequences left by the passage of Covid-19, so that its manifestations can result from any stage, being evidenced more frequently in cases that have undergone the most severe form of the disease. illness. Consequently, the lung damage caused by SARS-CoV-2 infection in the acute phase results from the combination of some expected clinical manifestations, such as: edema formation, alveolar release of epithelial cells and deposition of hyaline material in alveolar membranes . (POGLITSCH, *et al.* , 2020) . During the 2nd and 4th weeks, the lungs show signs of fibrosis, characterizing the next phase of the infection, where fibrin deposition occurs, infiltration of inflammatory cells and fibroblasts adjacent to the epithelial cells in the alveolar spaces (HULL, LLOYD, *et al.* , 2020) .

A little further on, during the 6th to 8th week, the lung tissue becomes fibrotic , in addition, bilateral lesions tend to be observed. In this context, Raghu and Wilson (2020) observed in their study that individuals, after hospital discharge, present restrictive abnormalities such as reduced diffusion capacity and small airway obstruction. Some authors also suggest that these abnormalities may be common in lung function, especially in individuals who have reached the most severe form of Covid-19, due to high inflammatory rates and pulmonary fibrosis.

Despite what is already evidence on the multisystem sequelae of Covid-19, several other studies are emerging around the sequelae left in the respiratory system after infection by the SARS-CoV-2 Coronavirus , suggesting that these may vary in individuals who have had it. mild, moderate or severe frames. The same authors also state that the resolution of the abnormalities may occur within the next 6 to 12 months after the infection, or even become permanent (HADAYA, BENHARASH, 2020) .

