## **2.3 Sample**

The sample will consist of 60 participants, divided into two groups: an intervention group (n=30) that will do a 12-week program, 2x/week of Pilates method exercises , and a control group (n=30) that will not do any intervention for rehabilitation in the period.

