## 2.5 Data analysis

### 2.5.1 Sample size (calculation or justification)

The sample size calculation was done with the “ pwr ” package (CHAMPELY S, 2018) (R package , version 1.2-2, <https://CRAN.R-project.org/package=pwr> ). For the calculation, we considered the mean of 41.3, the standard deviation of 5.05 and a minimal clinically important difference of 4.7 kg between the means of maximum load in the maximal voluntary contraction test (OLIVEIRA IO, 2016) and power based on *Cohen 's model* of 0.8 with a standard deviation of 5.05. Assuming  $\alpha = 0.05$ ,  $\beta = 0.8$ , standard deviation = 5.05 and an effect size proposed by Cohen of 0.93.

This effect size " *d* " is calculated by:

$$d = [(Reference\ average + Minimum\ detected\ change) - reference\ average] / deviation - standard$$

$$d = [( 41.3 + 4.7) - 41.3] / 5.05 \Rightarrow d = 0.93.$$

*pwr* package . in R we have:

```
n = pwr.t.test ( n=NULL, d=0.93, sig.level =0.05, power=0.8, type=" two.sample ", alternative="
two.sided ")
```

$$n = 19.15925$$

$$d = 0.93$$

$$sig.level = 0.05$$

$$power = 0.8$$

$$alternative = two.sided$$

In this way, we use on=established and rounded up to the first integer immediately higher ( $n=20$ ) + 20% to cover any losses. Thus, the minimum number of patients needed in each group will be 24 patients.

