### **2.5.5 Statistical analysis plan**

Data analysis will be performed using the SPSS 23.0 program ( Statistical Package for Social Sciences ). Descriptive analysis will be performed for all variables (mean and standard deviation). General Linear Model ( GLMs ) with mixed design will be performed to compare treatment effect size between groups. The pairwise comparison comparisons ) will be performed to verify the mean difference between the Pilates Group and the Control Group in all variables in each period independently.

Intention-to-treat analysis was used using the *Last method. observation Carried Forward* (LOCF) for lost participant data. A significance level of 0.05 and a confidence interval of 95% will be adopted

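### With one assessment before and one after, LOCF carries the baseline value forward and gives every lost patient zero change, which dilutes or biases the effect and can undercut the 12-week comparison

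*Combined protocol and SAP*

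**What the plan says.** Section 2.5.5 applies an intention-to-treat label and fills in missing outcomes by last "observation Carried Forward* (LOCF) for lost participant data". The Abstract repeats the rule: "using the Last Observation Carried Forward (LOCF) method for data on lost participants". No missing-data assumption, sensitivity analysis or alternative method is given.

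The timing of assessments is in the Summary: "All patients will be evaluated before and after for peripheral muscle strength and endurance, post-Covid-19 functional status, dyspnea, fatigue and quality of life". Chapter 2 describes no interim outcome visit. The Borg scale is recorded during sessions, but section 2.3.8 restricts it to controlling exercise intensity.

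The between-group analysis is a mixed-design general linear model followed by pairwise comparisons of the "mean difference between the Pilates Group and the Control Group in all variables in each period independently".

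Section 2.5.1 finds 20 patients per arm and adds "20% to cover any losses", reaching a minimum of 24 per arm (48 in total, as in the Summary). Section 2.3 gives a different total: "The sample will consist of 60 participants, divided into two groups", that is, 30 per arm.

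**The concern.** With two assessments, LOCF is baseline carried forward. Every patient lost before the second assessment is entered as unchanged, on every outcome. That is correct only if lost patients would neither have responded to Pilates nor have changed without it.

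Three things follow.

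- **Dilution.** If patients lost from the Pilates arm would have responded like completers, the estimated effect shrinks by the fraction lost.
- **Bias of uncertain direction.** If patients change without treatment and the arms lose different numbers, the estimate shifts. More loss in the control arm, which receives no rehabilitation, moves it towards a benefit that is not there. More loss in the Pilates arm moves it further towards no effect.
- **Power.** The 20% allowance works if about 20 observed values per arm are analysed. LOCF instead returns the lost patients to the comparison as pre-treatment values, and the sample size makes no allowance for that.

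The bias is present at any sample size. The power loss depends on the test, the number lost and the number randomised.

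**Working it through.** **Inputs from section 2.5.1.** Difference 4.7 kg, SD 5.05, two-sided test, "sig.level =0.05, power=0.8", 20 per arm plus 20%. **Assumptions, because the documents give no figures:** losses per arm, correlation r between the two visits, and gain g without treatment. Simulations used 20,000 runs per setting unless noted, SD 5.05 at both visits, and loss unrelated to outcome.

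**1. The plan's own figure.** d = 4.7 / 5.05 = 0.93. The two-sample t-test gives n = 19.16 per arm, as stated. Rounded up, 20 × 1.2 = 24. The result is reproduced, and 24 − 20 = 4 losses per arm use up the allowance.

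**2. Bias formula.** Let pT and pC be the fractions lost from Pilates and control, and δ the true effect. If the lost would have behaved like completers, the expected LOCF difference is (1 − pT)(g + δ) − (1 − pC)g. Hence

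bias = (pC − pT) × g − pT × δ.

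**3. Equal loss, 4 of 24 per arm.** 4.7 × 20/24 = 3.92 kg (simulated 3.91 to 3.93). With g = 0, the change-score 95% CI covers the true 4.7 kg in 93%, 92% and 90% of runs at r = 0.3, 0.5 and 0.7.

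**4. Power of the 12-week comparison, g = 0.** Under LOCF the Pilates-arm variance is 5.05² + f(1 − f) × 4.7², where f is the fraction lost. For f = 4/24 this is 25.50 + 3.07 = 28.57. The pooled SD is √((25.50 + 28.57)/2) = 5.20 and d = 3.92/5.20 = 0.75. With 24 per arm, power is 0.724.

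| Randomised per arm | Lost per arm | LOCF, formula | LOCF, simulated | Observed values only |
|---|---|---|---|---|
| 24 | 2 | 0.81 | 0.81–0.82 | 0.85 |
| 24 | 4 | 0.72 | 0.73 | 0.82 |
| 24 | 5 | 0.675 | 0.67–0.68 | 0.80 |
| 30 | 5 | 0.82 | 0.82–0.83 | 0.90 |
| 30 | 6 | 0.78 | 0.79 | 0.88 |

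Keeping 80% power under LOCF with one sixth lost would take about 29 per arm.

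**5. Power of the group-by-period (change) test, 24 per arm, 4 lost each, g = 0.**

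| r | LOCF | Observed values only |
|---|---|---|
| 0.3 | 0.67 | 0.68 |
| 0.5 | 0.81 | 0.82 |
| 0.7 | 0.95 | 0.96 |

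The cost is about one point. It grows if both arms improve: with g = 4 kg and r = 0.5, LOCF gives about 0.75 against about 0.82 (6,000 runs).

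**6. Unequal loss, true effect 4.7 kg, 6 (Pilates) v 2 (control) of 24 lost.** With g = 0, 4.7 − 0.25 × 4.7 = 3.5 kg. With g = 3 kg, the further shift is (2 − 6)/24 × 3 = −0.5, giving 3.0 kg.

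**7. Unequal loss, no true effect, 24 per arm.** Bias = (pC − pT) × g. The type I error range covers the post-value, change and ANCOVA tests on LOCF data at r = 0.5 to 0.7.

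| Lost, Pilates v control | Assumed g | False benefit | Type I error |
|---|---|---|---|
| 3 v 6 | 3 kg | 0.37 kg | 0.049–0.052 |
| 2 v 6 | 3 kg | 0.50 kg | 0.056–0.066 |
| 2 v 7 | 3 kg | 0.62 kg | 0.060–0.080 |
| 2 v 6 | 5 kg | 0.83 kg | 0.066–0.085 |
| 2 v 7 | 5 kg | 1.04 kg | 0.081–0.117 |
| 4 v 5 | 5 kg | 0.21 kg | 0.024–0.039 |
| 2 v 6 | 0 | 0 | about 0.05 |

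**8. Alternative.** ANCOVA on observed 12-week values, 4 lost per arm at random: mean 4.70 kg, coverage 0.95, power 0.84, 0.90 and 0.98 at r = 0.3, 0.5 and 0.7.

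**The case against.** **The power loss is narrow.** Section 2.5.5 names the mixed-design model first, and its group-by-period test loses about one point when untreated patients do not change. The 0.73 needs the whole allowance lost in both arms at 24 per arm, which section 2.5.1 calls a minimum. At 30 per arm with 5 lost there is no shortfall. This stands as a limit on the power claim. However, the 12-week two-sample comparison is the one the sample size was built on, and the plan commits to it.

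**LOCF may be nearer the truth than it looks.** Patients who leave a supervised programme may gain less. If those lost would gain half the effect and nobody changes untreated, the all-randomised effect is 4.7 × 20/24 + 2.35 × 4/24 = 4.31 kg. LOCF (3.92) and observed data (4.70) are then each off by 0.39 kg, in opposite directions. If the lost gain nothing, LOCF is right and observed data overstate by 0.78 kg. This is fair, and it is the reason for sensitivity analyses. It does not justify fixing one extreme as the only analysis.

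**The false-positive figures need strong assumptions.** The upper figure requires a 5 kg untreated gain, more than the trial's own important difference, and 2 v 7 lost. With a gain of 1 to 2 kg and 2 v 6 lost, type I error is 4.9 to 5.8%. The documents give no untreated strength gain. Section 1.1.8 concerns respiratory abnormalities and says resolution "may occur within the next 6 to 12 months after the infection, or even become permanent". Section 2.5.4 also delays entry until 90 days after discharge. The 5 kg rows should be read as extreme.

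**Scope.** The kilogram figures concern quadriceps load, one of four parts of the primary outcome. They do not transfer to the functional scale, grip or endurance, although the zero-change rule applies to all of them.

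**Conclusion.** The concern holds and should be fixed. LOCF here imputes zero change to every lost patient, with no stated justification and no sensitivity analysis. That rests on reading the two-visit schedule from the Summary and Abstract, which nothing in Chapter 2 contradicts.

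If the lost would have responded like completers, equal loss of 4 of 24 turns 4.7 kg into 3.9 kg, whichever test is used and at any trial size with the same fraction lost. Losses of 6 v 2 give 3.5 to 3.0 kg for an untreated gain of 0 to 3 kg. With no true effect, a false benefit needs both untreated change and heavier control-arm loss: 0.4 to 1.0 kg, with type I error of 5 to 12%, over gains of 3 to 5 kg and losses of 2–3 v 6–7. LOCF therefore cannot be defended as reliably conservative.

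The power shortfall is conditional. It is clear for the 12-week comparison at 24 per arm with the allowance used up (about 0.73 against a target of 0.80), and largely absent at 30 per arm. Which number applies cannot be settled until the 48 and the 60 are reconciled.

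**What to change.** In section 2.5.5, the Summary and the Abstract, remove LOCF as the primary rule and specify the following.

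- **Primary analysis:** a baseline-adjusted comparison of all randomised patients with a 12-week value, in the arm assigned (ANCOVA or SPSS MIXED). MIXED with both visits as outcomes also keeps patients who have only a baseline value.
- **Sensitivity analysis:** multiple imputation by arm, with a reference-based version for the case in which lost patients gain nothing from Pilates. LOCF may stay only as a labelled sensitivity run.
- **Reporting:** number lost and reasons, by arm.

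The cost is SAP wording and a few lines of SPSS syntax. The drawback is that the primary analysis relies on data being missing at random given arm and baseline, which cannot be tested either. The sensitivity analyses show how far the result depends on it.

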### 2.5.6 Availability and access to data

All data may be made available for consultation and *full access* at the clinical trial registration site.

## 2.6 Expected results

The hypotheses of this clinical trial hope to demonstrate the clinical effects of a Pilates program for the management of musculoskeletal disorders and persistent symptoms in patients with COVID-19. Studies involving other populations have already demonstrated the effects of Pilates on peripheral muscle strength and *endurance* in patients with chronic lung disorders, patients with chronic low back pain, patients with neurological syndromes, among others. Thus, it is hypothesized that similar effects may occur in the study population.

## 2.7 Budget and financial support

This study will be entirely with own resources and equipment available in the research laboratories of the teaching institution partner in conducting the study. There is no burden to study participants

**Table 3: Budget details.**

Budget identification	Type	Price R\$)
Physiotherapist specializing in Pilates	execution team	BRL 0.00
reformer	permanent material	BRL 0.00
Cadillac	permanent material	BRL 0.00

Chair	permanent material	BRL 0.00
Lader barrel	permanent material	BRL 0.00
pulse oximeter	permanent material	BRL 0.00
stopwatch	permanent material	BRL 0.00
palm grip dynamometer	permanent material	BRL 0.00
Extension chair and load cell	permanent material	BRL 0.00
Video camera	permanent material	BRL 0.00
Reproduction of evaluation sheets	Material consumption	BRL 50.00
A4 paper format	Material consumption	BRL 50.00
	Total in BRL	BRL 100.00

## 2.8 Timeline

**Table 4: Execution schedule.**

step identification	Start (mm/yy)	Term (mm/yy)
Beginning of the course and designing the project	August/20	November/21
Project submission to the Research Ethics Committee	April/22	April/22
Methods training	April/22	April/22
patient recruitment	April/22	May/22
Execution of the Protocol	April/22	July/22
Data collection and tabulation	April/22	July/22
Data analysis	July/22	August/22
Preparation of the manuscript(s)	August/22	August/22
Final essay writing	August/22	August/22
defense exam	September/22	September/22
Changes guided by the examining board	September/22	September/22
Submission of manuscript(s)	September/22	October/22
Delivery of the final version of the final paper	October/22	October/22

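### The calendar recruits through May/22 but closes the 12-week programme and data collection in July/22, so starts after about 8 May do not fit it

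*Combined protocol and SAP*

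**What the plan says.** Section 2.8, Table 4, gives start and end months for each step. Four rows matter here, including the one for "Execution of the Protocol":

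- "patient recruitment April/22 May/22"
- "Execution of the Protocol April/22 July/22"
- "Data collection and tabulation April/22 July/22"
- "Data analysis July/22 August/22"

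Section 2.3 describes the intervention group as one "that will do a 12-week program, 2x/week of Pilates method exercises", and section 2.5.3 repeats the 12-week length. The Summary and Abstract provide for assessment before and after the programme only. Section 2.5.5 plans an intention-to-treat analysis with last observation carried forward; the rule is worded "LOCF) for lost participant data".

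No section gives a last start date, provides for follow-up after July/22, or says how a participant still in the programme at the end of July would be handled.

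**The concern.** Recruitment may run to the end of May, yet only two months separate that date from the end of July and the programme needs almost three. Someone recruited in the second half of May cannot complete 12 weeks inside the stated execution and data-collection window.

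The outcome of the later starters is at stake. If July were treated as a firm close, there are two possibilities. They could be assessed before 12 weeks, which mixes follow-up times and treatment exposure. Or they could have no post-test. With only one assessment after baseline, carrying the last observation forward would then enter the baseline value as the outcome, that is, no change. Either route would be expected to shrink the difference between the arms, by very different amounts.

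**Working it through.** **The plan's own figure.** Section 2.5.1 uses d = 4.7 / 5.05 = 0.93, two-sided alpha 0.05 and power 0.80. The two-sample t-test solution is n = 19.16, rounded up to 20; 20 × 1.2 = 24 per group. This reproduces. At 24 per group, d = 0.93 gives 88% power. Section 2.3 states 30 per group, which gives 94%.

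**Calendar check.** Table 4 has month resolution, so each end month is taken to its last day, the reading most generous to the plan.

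- Programme length: 12 × 7 = 84 days.
- Latest start for day 84 to fall by the close: 31 July 2022 − 84 days = 8 May 2022.
- Finish for the last possible recruit: 31 May 2022 + 84 days = 23 August 2022.
- Time available to a 31 May start: 61 days to 31 July, 61 / 7 = 8.7 weeks.
- If testing directly follows the 24th session, that session falls 78 to 81 days after the first (11 × 7 plus a gap of 1 to 4 days). The latest start is then 11 to 14 May.

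**Does the eligibility wait change this?** No. Section 2.3.2 limits discharges to August to December 2021, and section 2.5.4 requires 90 days after discharge. 31 December 2021 + 90 days = 31 March 2022, before recruitment opens.

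**Share affected.** This is an assumption, because the documents give no accrual pattern. With even daily accrual from 1 April to 31 May, there are 61 days, of which 9 to 31 May are 23: 23 / 61 = 38%. With the later cut-off of 11 to 14 May, 17 to 20 of the 61 days remain too late, 28% to 33%.

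**Effect on power.** Late starters are spread equally over the arms and the SD is held at 5.05.

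- *Tested early, effect assumed linear in time.* Late starters have 61 to 83 days, mean 72. The average effect is multiplied by 0.623 + 0.377 × 72/84 = 0.946, so d = 0.93 × 0.946 = 0.88.
- *All carried forward from baseline.* The average effect is multiplied by 1 − 0.377 = 0.623, so d = 0.93 × 0.623 = 0.58. The 4.7 kg difference becomes 4.7 × 0.623 = 2.9 kg.

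| Handling of late starters (38%) | d | Power, 24 per arm | Power, 30 per arm |
|---|---|---|---|
| None late | 0.93 | 88% | 94% |
| Tested early, linear effect | 0.88 | 85% | 92% |
| Carried forward from baseline | 0.58 | 50% | 60% |

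**The case against.** The strongest reply is that Table 4 is a planning schedule for an academic project, with rows for the course and the defence exam, and is stated in months. A last start on or before 8 May still falls in May/22 and satisfies the table as printed. So the table does not force a contradiction; it permits an infeasible schedule and does not exclude it. That part of the reply stands.

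A reader might infer more than the documents support:

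- *That late starters would be carried forward from baseline.* No section makes July an administrative cut-off, and the carry-forward rule is for lost participants. Someone still attending sessions is not lost. Slippage of a few weeks is also possible and would do no statistical harm.
- *That power would fall to 50%.* That is the worst case, with even accrual, zero effect in every late starter and 24 per arm. The eligible pool is closed and has cleared the 90-day wait before April, so early recruitment is equally possible.
- *That outcomes would be examined before follow-up ends.* Collection ends and analysis begins in the same month, so one may follow the other. No interim comparison is planned.
- *That April ethics submission makes the late share larger.* This holds only if approval delays enrolment while the May and July end dates stay fixed, which the documents do not say.

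The reply does not remove the gap. The table allows recruitment through all of May, and nothing else in the protocol limits starts or extends collection. Testing straight after the last session moves the cut-off by only three to six days.

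**Conclusion.** The point holds as a calendar inconsistency. The full recruitment window, the 12-week programme and a July close do not fit together: starts after 8 May (about 11 to 14 May at the latest) overrun, by up to 23 days for a 31 May start. This rests only on Table 4 and the 12-week length.

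The consequence is conditional. It arises only if the calendar is enforced, and its size depends on accrual and on handling, neither of which is stated. With even accrual from 1 April, power at 24 per arm would lie between about 50% and 85%, against 88%; at 30 per arm the worst case is about 60%. These figures show scale and are not a forecast. The sample-size calculation itself is not affected.

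**What to change.** Reconcile Table 4 with the 12-week design in one of two ways:

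1. Extend execution and data collection to the end of August/22, and start analysis only after the last 12-week assessment.
2. Keep the July close and state 8 May as the last start date.

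In either case, add a sentence to section 2.5.5 saying that no participant is assessed early, or treated as lost, because the calendar has ended.

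The first option moves the analysis and writing steps by about 3 to 4 weeks. The second shortens the recruitment window by about three weeks. Neither changes the intervention or the outcomes.
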